Experimental data support the potential radiosensitizing effect of HBO in intracranial tumors (characterized by large hypoxic fractions) while having little effect on normal tissues (with normal oxygen levels). Four clinical trials have evaluated the radio-sensitizing potential of hyperbaric oxygen in malignant gliomas. This technique was found to be feasible [2], involved minimal toxicity on normal tissues [3, 4], and improved outcomes [5, 6]. A recent review of hyperbaric oxygen as a radiosensitizer concluded, “... *given the findings of improved tumor control and mortality..., there is a case for large randomized trials of high methodological vigor...*” [7].

Although HBO has been studied in conjunction with XRT in the treatment of primary brain tumors, no prior study has examined the role of HBO in combination with XRT in the treatment of tumors (“secondary”) metastatic to the brain. Furthermore, no prior study has studied HBO in conjunction with stereotactic radiosurgery (SRS).

Characterized by the delivery of millimeter-accurate, high-dose radiation therapy in a single fraction to a small volume of target tissue, SRS is the standard of care for the

treatment of small brain metastases. It is safe and efficacious in a wide variety of clinical situations. Local control rates at one year following SRS range from 50-90%, with tumor size a significant prognostic factor (Figures 4 and 5).

Figure 4. Kaplan-Meier analysis of freedom-from-local recurrence (LR) stratified by tumor size for a large population of patients with intact brain metastases treated with SRS [8].

[figure not shown]

FIG. 1. Graph showing cumulative tumor progression-free survival curves, based on tumor size. The maximum lesion diameters are provided. The mean prescribed doses were 20.6 Gy in 8573 tiny, 20.3 Gy in 977 small, 19.2 Gy in 441 medium, and 15.7 Gy in 172 large lesions. The tumor control rates at 1 year were 99.5% in tiny, 92.6% in small, 87.3% in medium, and 65.5% in large lesions. Differences were statistically significant ($p < 0.0001$).

Figure 5. Kaplan-Meier analysis of freedom-from-local recurrence (LR) stratified by pre-operative tumor diameter at 3.0 cm: recent DHMC experience [9].

[figure not shown]

Table 1. One-year and two-year outcomes stratified by tumor size: recent DHMC experience [9].

Table 1 Incidence as a function of tumor size

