3.1 Inclusion Criteria

Patients meeting all the following criteria are eligible for this trial:

- Metastatic brain tumor referred to radiation oncology for treatment
- Size of the presenting metastatic lesion up to 5.0 cm diameter
- Age \geq 18 years
- Patients must give informed consent indicating they are aware of the investigational nature of this treatment
- Karnofsky Performance Status \geq 70% (Zubrod score 0 to 1)
- Women of childbearing potential must have a negative serum or urine pregnancy test within 14 days to start of study therapy
- CBC and CMP within 30 days to start of study therapy

- Chest imaging (Chest Xray or Chest CT) within past 12 months, that does not show any contraindication to hyperbaric therapy (if patient has had any thoracic surgery or other significant event that might have affected the thorax such as trauma, pneumothorax, chest tube insertion, pleurodesis, or thoracentesis and has not had imaging since that event, then the imaging should be repeated).
- Neurosurgery Consult

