For the secondary endpoints, using Cox proportional hazards models, and Kaplan-Meier survival statistics, the overall group of 20 will be analyzed for event-free survival and compared against a matched set of patients from our institution (see below for methodology). This match will be based on tumor size, resection status, and histology-specific graded prognostic assessment (GPA). The GPA is a validated, widely accepted prognostic scale predictive of survival for patients presenting with brain metastases. Diagnosis-specific GPA calculation is based on published criteria including tumor histology, presence of systemic metastases, number of brain metastases, age, performance status, and breast-cancer specific molecular markers [29-31]. Further demographic and treatment data will also be collected, including: gender, subtotal resection versus gross total resection (if tumor resected), tumor diameter (prior to first treatment, whether surgery or SRS), SRS target volume (PTV), and prescribed dose to the PTV. The secondary outcome variables will be the first occurrence of the event of interest and also the time until the first occurrence of the event of interest. These events include: intracranial recurrence at SRS site, intracranial recurrence at a distant site, whole brain XRT, second SRS (classified as either local or distant), third SRS (classified as local or distant), radionecrosis at the SRS site, and death.

A retrospective database pertaining to Dartmouth-Hitchcock's experience with stereotactic radiosurgery in the treatment of brain metastases is being collected through Study 00030625 (PI [name]). Pertinent matching variables, along with demographic variables, treatment variables, and outcome variables for the control population are available on 00030625. The matching variables (histology, lesion size, resection status, and calculated GPA) will be used to identify a control population in the Study 00030625 that match 1:1 against the D12129 enrolled patient population.

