Specifically, patients with similar tumor histologies will be matched against histologies found in the D12129 patient population, falling into one of six categories: (1) non-small cell lung cancer, (2) melanoma, (3) breast cancer, (4) renal cell cancer, (5) GI cancers, and (5) other histologies. Once a histologic match is identified, the patient is then matched by resection status (either unresected or resected). The third matching variable is then GPA. If an exact GPA match is not available in the 000030625 data base, then a patient with a higher GPA will be selected, with the control patient's GPA as near as possible to that of the corresponding D12129 patient (thereby, if anything, biasing the survival outcome data slightly against the D12129 data set). Lastly, the fourth matching variable is tumor size (i.e. maximum tumor diameter) at time of treatment (a categorical variable, either below or above 2.0 cm). If an exact match for the fourth variable is not available in the 000030625 data base, then size will be matched as closely as possible to the 2.0 cm cut-off from those patients available in this historical database. These

matching patients identified in 000030625 data base will serve as the control group for the D12129 study.

Once the control group patients have been selected, their data will be extracted from the 000030625 database in de-identified form. These data will be reviewed by an “honest broker” to assure proper de-identification and HIPAA compliance. These de-identified control group data will then be merged with the D12129 dataset. Analysis of this combined data base then will allow comparison of HBO-treated and control patients in terms of event-specific outcome parameters, with events including: death, local intracranial recurrence, distant intracranial recurrence, whole brain radiation therapy, and repeat SRS (either local or distant).

Exploratory variables will include QOL data and tumor markers. Comparisons for change in markers before versus after HBO-SRS treatment will be performed for the entire group of twenty patients. Also comparisons will be performed for subgroups (including comparisons of those with resections versus those without, and of those above 2.0 cm diameter versus those below).

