6.2 Sample Size Determination

For the initial phase of this study we anticipate enrolling 20 patients (DHMC treats about 80-100 SRS patients yearly): 5 with resected lesions up to 2.0 cm (diameter), 5 with intact lesions up to 2.0 cm, 5 with resected lesions greater than 2.0 cm, and 5 with intact lesions greater than 2.0 cm. Based on a median event-free survival time of 6 months in the control group, a log-rank test with a one-sided significance level of 0.05 and a power of 0.80 can detect a relative risk of 0.39 or smaller. Thus, we have sufficient power to detect 61% increase in the risk of toxicity, recurrence or death.

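### Size is matched only as below or above 2.0 cm, and no rule chooses among tied controls, which leaves the secondary comparison open to avoidable size imbalance and discretionary selection

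*Combined protocol and SAP*

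**What the plan says.** Section 6.1 draws 1:1 controls from the institution's retrospective radiosurgery database in a fixed order: histology group, resection status, GPA (the nearest higher value if there is no exact match), then size. On size it says that "the fourth matching variable is tumor size (i.e. maximum tumor diameter) at time of treatment (a categorical variable, either below or above 2.0 cm"). If no exact match on this variable exists, "size will be matched as closely as possible to the 2.0 cm cut-off from those patients available in this historical database".

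Section 3.1 admits "Size of the presenting metastatic lesion up to 5.0 cm diameter". The Section 6.2 enrolment plan includes "5 with resected lesions greater than 2.0 cm, and 5 with intact lesions greater than 2.0 cm", which is 10 of 20 patients.

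On the database, Section 6.1 says that "treatment variables, and outcome variables for the control population are available on 00030625". It then says: "Once the control group patients have been selected, their data will be extracted from the 000030625 database in de-identified form". An honest broker reviews the extracted data for de-identification and HIPAA compliance.

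The further data to be collected include "tumor diameter (prior to first treatment, whether surgery or SRS), SRS target volume (PTV), and prescribed dose to the PTV". The secondary analysis uses Cox models and Kaplan-Meier statistics, and no covariates are named.

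**The concern.** The size category above 2.0 cm spans 3.0 cm of diameter. Within it the plan treats all controls as equally good matches and is silent on how to choose among them. Two things follow. The arms can differ in size inside the category even though every patient and control has a recorded diameter. And the person choosing has discretion, with outcomes held in the same database and no statement that they are hidden during selection.

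The protocol itself regards size as prognostic. Section 1.1 hypothesises that the benefit of HBO grows with lesion size and shows local control falling as size rises. The general dose table in Section 5.3.7 has three bands above 2.0 cm, so a size mismatch can also be a dose mismatch. The secondary objective is non-inferiority to these controls, and the events include local recurrence, radionecrosis and death.

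Diameter is also worded in two ways. It is taken at the time of treatment for matching, but before first treatment (surgery or SRS) for data collection. These may differ for the 10 planned resected patients. The institution's own series in Section 1.1 was "stratified by pre-operative tumor diameter at 3.0 cm".

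**Working it through.** **1. The plan's own figure.** Section 6.2 states a detectable relative risk of 0.39 (20 v 20, one-sided 0.05, power 0.80, control median 6 months). Assume exponential survival, 24 months of follow-up and Freedman's formula.
- Expected events at HR 0.389: 20 × (1 − 2^(−4)) + 20 × (1 − 2^(−4 × 0.389)) = 18.75 + 13.2 = 32.0.
- Events needed: (1.645 + 0.842)² × (1.389/0.611)² = 32.0.

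The figure reproduces. The point concerns comparability of the arms and leaves the sample size unchanged.

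**2. Does the fallback misdirect?** The fourth variable is defined as categorical, so an exact match means the same category. The fallback then applies only when every remaining candidate lies across 2.0 cm from the patient. Take a patient of diameter x > 2.0 and a candidate c ≤ 2.0:

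x − c = (x − 2.0) + (2.0 − c).

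The first term is the same for all candidates, so the candidate nearest 2.0 cm is also nearest x. The argument is symmetric for a small-lesion patient. In 100,000 simulated cases the two rules never chose differently.

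**3. What would a tie-break on diameter do?** The documents give neither the pool size nor the diameter distribution, so two assumed distributions for lesions above 2.0 cm were simulated:
- A: 14 lesions at 2.1-3.0 cm to 20 at 3.1-5.0 cm, uniform within each band. The counts come from Table 1 (34 above 2.0 cm, of which 20 above 3.0 cm).
- B: 2 + 3 × Beta(1.5, 2) cm.

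| Tied controls | Mean pair gap, A (cm) | Mean pair gap, B (cm) |
|---|---|---|
| 1 (or arbitrary choice) | 1.00 | 0.80 |
| 2, nearest taken | 0.62 | 0.51 |
| 3, nearest taken | 0.44 | 0.37 |

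Under A, the share of pairs straddling 3.0 cm falls from 48% to 29% or 18%.

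**4. Can the direction be predicted?** Only crudely. Subtracting Kaplan-Meier percentages in Table 1 (resected lesions only) gives implied values for the 14 patients at 2.1-3.0 cm:
- Freedom from local recurrence, 2 years: (29 × 0.891 − 15 × 1.000)/14 = 0.774, or (34 × 0.513 − 20 × 0.404)/14 = 0.669, against 0.404 above 3.0 cm.
- The same at 1 year: 0.774 or (34 × 0.792 − 20 × 0.807)/14 = 0.771, against 0.807.
- Survival, 1 year: (29 × 0.513 − 15 × 0.692)/14 = 0.321, or (34 × 0.466 − 20 × 0.550)/14 = 0.346, against 0.550.

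The larger lesions look worse for 2-year local recurrence, no worse at 1 year, and better for survival. The intact series in Section 1.1 shows 87.3% v 65.5% one-year control in medium v large lesions, but the band limits are in a figure not available here.

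**5. Could Cox adjustment replace the tie-break?** Allow for death with piecewise-constant, independent hazards fitted to Table 1. The 2-year cumulative incidence of local recurrence is then 0.247 above 2.0 cm and 0 at or below it, and 0.185 for all subjects. Expected recurrences in 40 patients are 0.247 × 20 = 4.9 or 0.185 × 40 = 7.4. That is too few for a precise adjusted model.

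**The case against.** The 2.0 cm cut is a defensible choice. It is the enrolment stratum, the planned subgroup cut and a cut-off in Table 1 with a sharp contrast (100% v 51.3% free of local recurrence at 2 years). Ranking GPA above size is reasonable when death and distant recurrence are among the events. Ties must survive histology, resection status and GPA, so there may be few. The Cox models name no covariates at all, so diameter has not been singled out for neglect. The two diameter wordings may mean the same thing. All of this stands, and it is why the matching order and the category should stay and the priority is low. None of it supplies a rule for choosing among the ties that do occur.

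A reader might infer more than the documents support:
- *The fallback pulls controls towards 2.0 cm.* It would do so only if an exact match meant the same diameter. The text calls the variable categorical, and step 2 shows the fallback then picks the nearest diameter anyway.
- *A definite bias in recurrence or survival can be stated.* Purely random imbalance is noise that the test variance already reflects. Pairs that cross 2.0 cm come from ranking size last, which the fix keeps. The subtractions in step 4 rest on 14 patients and Kaplan-Meier estimates that do not subtract exactly, so they show only that the direction is unclear.
- *Controls will be chosen knowing their outcomes.* The plan does not say so. It only fails to exclude it, and the honest broker's stated task is de-identification after selection.

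**Conclusion.** The point holds for choice within the size category. Size is matched last and in two classes, no rule uses diameter among tied controls, no upper size limit for controls is stated, and selection is not said to be blind to outcome. The resulting imbalance and discretion can be partly avoided because diameter is already collected.

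The effect on the secondary outcomes cannot be quantified from the documents. What can be shown, assuming 2 or 3 tied controls and the size distributions above, is a fall in the mean within-pair gap from about 0.8-1.0 cm to about 0.5-0.6 or 0.4 cm. Where only one control is available nothing improves. The direction of any bias is unknown. The fallback to the 2.0 cm cut-off needs no change, and the primary feasibility endpoint is untouched. This is a cheap improvement of low priority.

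**What to change.** Keep the matching order, the 2.0 cm category and the fallback. Add to Section 6.1:

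> Among controls tied on histology, resection status, GPA (exact, or nearest higher where that rule applies) and size category, the control whose maximum diameter is nearest the patient's own is selected. Controls are limited to lesions up to 5.0 cm and are selected by existing staff without sight of outcome data.

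Reconcile the two diameter wordings into one definition for matching and data collection. Tabulate diameter by arm. Report a diameter-adjusted Cox model as a sensitivity analysis only.

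The cost is a few lines of text and slightly more extraction work. Sample size and schedule do not change. The downside is that the sensitivity model will be imprecise, with about 5-7 local recurrences expected, and should be presented as such.

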7.1 Definitions

Unanticipated Problems Involving Risk to Subjects or Others

Any incident, experience, or outcome that meets all of the following criteria:

- Unexpected in nature, severity, or frequency (i.e. not described in study-related documents such as the IRB-approved protocol or consent form, the investigators brochure, etc)

- Related or possibly related to participation in the research (i.e. possibly related means there is a reasonable possibility that the incident experience, or outcome may have been caused by the procedures involved in the research)
- Suggests that the research places subjects or others at greater risk of harm (including physical, psychological, economic, or social harm).

Adverse Event

An **adverse event** (AE) is any symptom, sign, illness or experience that develops or worsens in severity during the course of the study. Inter-current illnesses or injuries should be regarded as adverse events. Abnormal results of diagnostic procedures are considered to be adverse events if the abnormality:

- results in study withdrawal
- is associated with a serious adverse event
- is associated with clinical signs or symptoms
- leads to additional treatment or to further diagnostic tests
- is considered by the investigator to be of clinical significance

Solicited Adverse Event

A **solicited adverse event** is any adverse event that has been identified by the PI or co-PIs as potentially related to intracranial SRS and/or HBO treatments. Occurrence and severity of all solicited adverse events will be catalogued for all D12129 patients. These are enumerated in Attachment 14.6.

Serious Adverse Event

Adverse events are classified as serious or non-serious. A **serious adverse event** is any AE that is:

- fatal
- life-threatening
- requires or prolongs hospital stay
- results in persistent or significant disability or incapacity
- a congenital anomaly or birth defect
- an important medical event

Important medical events are those that may not be immediately life threatening, but are clearly of major clinical significance. They may jeopardize the subject, and may require intervention to prevent one of the other serious outcomes noted above. For example, drug overdose or abuse, a seizure that resulted in in-patient hospitalization, or intensive treatment of bronchospasm in an emergency department would typically be considered serious.

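### Section 6.2 claims comparative power for toxicity, but Section 6.1 lists no general toxicity event and no toxicity ascertainment is described for the historical controls

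*Combined protocol and SAP*

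**What the plan says.** - **Power (Section 6.2).** The calculation is "Based on a median event-free survival time of 6 months in the control group", with "a log-rank test with a one-sided significance level of 0.05 and a power of 0.80", and it "can detect a relative risk of 0.39 or smaller". The conclusion drawn is "Thus, we have sufficient power to detect 61% increase in the risk of toxicity, recurrence or death".
- **Endpoint (Section 2.3).** Symptomatic treatment toxicity is the first endpoint listed under the aim of showing non-inferiority to historical controls. Section 7.4 also ties adverse events to the non-inferiority endpoint.
- **Analysis (Section 6.1).** Event-free survival is to be compared with matched controls by Cox and Kaplan-Meier methods, but its components are not stated. The same paragraph lists events of interest: local and distant recurrence, whole brain radiotherapy, second and third SRS, "radionecrosis at the SRS site, and death". Radionecrosis is the only toxicity in that list. A later paragraph describes the merged-data analysis as a "comparison of HBO-treated and control patients in terms of event-specific outcome parameters, with events including: death, local intracranial recurrence, distant intracranial recurrence", then adds whole brain radiotherapy and repeat SRS. Neither general toxicity nor radionecrosis appears there.
- **Toxicity capture.** Section 7.1 says "Occurrence and severity of all solicited adverse events will be catalogued for all D12129 patients". Section 7.2 adds specific questioning at every contact, CTCAE v4.0 grading and a chart review to catch missed events. Controls come from the retrospective database of Study 00030625, whose outcome variables are said to be available but are not itemised.

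**The concern.** Non-inferiority is one of only two stated objectives, and toxicity is the outcome on which a reader would most want reassurance. Section 1.5 itself reports an odds ratio of 2.43 for radiation-related complications with HBO in head-and-neck trials, while noting confounding.

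A sentence claiming enough power to detect increased toxicity invites a null comparison to be read as evidence of safety. That reading needs toxicity to be an event in the comparison and to be ascertained alike in both groups. The documents describe neither. Because event-free survival is undefined, an analyst could also decide whether toxicity counts after seeing the data.

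**Working it through.** **1. The stated figure and what goes into it.** Inputs: 20 trial patients (Section 6.2), 20 controls from 1:1 matching (Section 6.1), control median 6 months, one-sided 0.05, and 24 months of follow-up (Section 5.4). Section 6.2 names neither its formula nor its follow-up, so the Freedman formula with exponential survival is an assumption.

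- Control hazard: ln 2 / 6 = 0.1155 per month. HBO hazard at a ratio of 0.39: 0.0451.
- Event probabilities by 24 months: 1 − exp(−0.1155 × 24) = 0.9375 and 1 − exp(−0.0451 × 24) = 0.661.
- Expected events: 20 × (0.9375 + 0.661) = 32.0.
- Power: Φ(√32.0 × (1 − 0.39)/(1 + 0.39) − 1.645) = 0.80.

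The 0.39 is reproduced. It is a generic 20-versus-20 log-rank calculation resting on one control median. It has no toxicity input: no rate, no grade threshold and no time window.

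**2. Toxicity, place by place.**

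| Place | General toxicity | Radionecrosis |
|---|---|---|
| 2.3, non-inferiority endpoints | listed | listed |
| 6.1, events of interest | absent | listed |
| 6.1, HBO versus control analysis | absent | absent |
| 6.2, power sentence | claimed | not named separately |
| 7.1 and 7.2, adverse event capture | described for trial patients | – |
| Control database | not itemised | not itemised |

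Section 14.6 includes barotrauma among the solicited events. Controls received no HBO and so cannot have HBO barotrauma. Even complete control records would not make a composite of all solicited events symmetric.

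**3. What would follow if the Section 6.2 wording were applied to the trial data.** This is illustration only. Assume that the 6-month control median contains no toxicity, that toxicity is counted in the HBO group alone, that hazards are constant and independent, and that a proportion q of HBO patients would have a counted toxicity by 12 months. The documents give no toxicity rate, so q = 10% to 40% is assumed.

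Added hazard = −ln(1 − q)/12. Apparent hazard ratio = true ratio + added hazard/0.1155.

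| q at 12 months | Added hazard | Apparent ratio, true 1.00 | False signal of harm | Apparent ratio, true 0.39 | Power |
|---|---|---|---|---|---|
| 0 | 0 | 1.00 | 5.5% | 0.39 | 0.80 |
| 10% | 0.0088 | 1.08 | 8% | 0.47 | 0.68 |
| 20% | 0.0186 | 1.16 | 12% | 0.55 | 0.52 |
| 30% | 0.0297 | 1.26 | 18% | 0.65 | 0.36 |
| 40% | 0.0426 | 1.37 | 25% | 0.76 | 0.21 |

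The false-signal column comes from 20,000 simulated trials per row (20 versus 20, 24-month follow-up, one-sided 0.05 log-rank test). The power column uses the formula in step 1 with the apparent ratio put in.

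**The case against.** A reader might infer that the plan counts toxicity in the HBO group and not in the controls, and so builds in a bias. The documents do not support that as fact. Both event lists in Section 6.1 can be read as leaving general toxicity out of both groups, and toxicity enters the powered event only through the last sentence of Section 6.2. The table in step 3 needs a construction that no section specifies: a control median free of toxicity, with toxicity then added for HBO alone. Had the median been meant to include toxicity, it would already carry control toxicity.

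Nor do the documents say that controls lack toxicity data. The contents of Study 00030625 are not itemised, and the list for the HBO versus control analysis is open-ended, so radionecrosis may well be intended there. Safety oversight does not depend on this comparison either: toxicity is graded for every treated patient, reviewed quarterly and subject to a stopping rule in Section 7.4.

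All of this stands, and it limits the point. It does not rescue the claim. If toxicity is outside the comparison, Section 6.2 has no basis for claiming power on it. If it is inside, the ascertainment described is unequal.

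**Conclusion.** The claim of comparative power for toxicity, and of non-inferiority on it, has no basis in the design as described. This conclusion rests on setting the sections side by side, not on any assumed rate.

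One-sided counting is a possibility, not a stated feature of the analysis. The range of 1.08 to 1.37 shows how large the distortion against HBO would be under the assumptions in step 3; it is not an estimate of bias in this trial. The absence of control toxicity data is likewise inferred from silence. The radionecrosis mismatch between the two lists in Section 6.1 is a matter of alignment.

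The secondary objective is affected; primary feasibility is not. Describing a relative risk of 0.39 as a 61% increase is a separate error in the same sentence (0.39 is a 61% reduction), and deleting toxicity does not cure it.

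**What to change.** 1. **Section 6.2:** delete toxicity from the power sentence.
2. **Sections 2.3 and 6.1:** report HBO-group toxicity descriptively, with exact confidence intervals and no non-inferiority claim.
3. **Section 6.1:** define event-free survival once, using only components ascertained the same way in both groups. Local recurrence, distant brain recurrence or death is one workable choice, since all three are already listed for the control comparison.
4. **Radionecrosis:** establish whether Study 00030625 records it. If so, add it to the HBO versus control list so that the two lists in Section 6.1 agree. If not, make no comparative claim for it.

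The cost is SAP wording and one check of the control database; no further patients are needed. The downside is that the toxicity conclusion becomes descriptive, and with 20 patients it will be imprecise: even with no events of a given kind, the exact one-sided 95% upper limit is 1 − 0.05^(1/20) = 13.9%.
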